If non-inferiority is demonstrated: to compare the efficacy of an early management strategy using 8% capsaicin topical treatment with that of standard oral pregabalin therapy on the evolution of ICBN after 2 months of treatment in patients who have undergone surgical excision for breast cancer.	The 11-point Numerical Rating Scale (NRS) for pain is collected at randomization (T0) and at Month 2 (T2) (see primary endpoint).	2 months
To compare the efficacy of an early management strategy using 8% capsaicin topical treatment (experimental arm) versus standard pregabalin therapy (control arm) on the evolution of ICBN after 6 months of treatment in patients who have undergone surgical excision for breast cancer.	The 11-point Numerical Rating Scale for pain is also collected at Month 6 (T6).	6 months
To compare patient-reported functional changes (activities, symptoms, emotions,	The PGIC, QLQ-C30, QLQ-BR23, and EQ-5D questionnaires are administered at T0, T2, and	6 months

and quality of life) between the two arms after 2 and 6 months of treatment.	T6 to assess functional changes and patient-reported quality-of-life outcomes in both treatment arms.	
To compare the reduction of the painful area between the two arms after 2 and 6 months of treatment.	The painful area is measured using pain mapping at baseline (T0), and after 2 months (T2) and 6 months (T6) of treatment. The surface area corresponds to the zone enclosed within the drawn boundaries of the painful region (centralized review).	2 months
To assess the safety profile of each treatment by collecting adverse events in each study arm.	Treatment tolerability will be assessed based on the number of patients experiencing at least one adverse event of grade ≥ 2 according to CTCAE v5.	6 months
To compare weight change between the two arms after 6 months of treatment.	Weight is collected at T0, T2, and T6.	6 months
In the capsaicin arm only, to estimate the proportion of patients for whom a single application was sufficient.	In the capsaicin arm, the number of applications and the total number of patches received by each patient during the 6-month period will also be recorded.	6 months
To assess the impact of anxiety and depression on treatment response for ICBN after breast cancer surgery.	The HADS questionnaire is collected at baseline, T2, and T6.	6 months

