The screening period extends from 3 months before surgery to 12 months after breast cancer surgery. Patients who agree to participate are scheduled for a screening visit between 3 and 12 months post-surgery. If they present with ICBN, defined by a DN4 score ≥ 4 , they will be included and randomized to receive either pregabalin (standard treatment) or topical capsaicin patch (experimental treatment), both of which are indicated for the management of peripheral neuropathic pain.

Pregabalin will be initiated with a gradual titration to reach a dose of 600 mg/day in two divided doses, depending on patient tolerability.

Capsaicin patches will be applied in a hospital setting to the painful area for 1 hour, with applications scheduled every 90 days.

All patients will undergo assessments at T0 (± 7 days) and T6 (± 7 days) regarding pain evolution (intensity and area), treatment tolerability, and quality of life.

The end of treatment and study follow-up is planned at the final pain-evaluation visit (T6).

F) STATISTICAL CONSIDERATIONS

SAMPLE SIZE DETERMINATION	
Statistical analyses will be performed using R software.
 
A total of 772 patients will be included, allocated into two balanced groups.
 
Sample size calculation
 
An interim analysis is planned once 300 patients have been included (minimum 150 per arm), based on the primary endpoint.
 
Alpha allocation:
 
 - 0.005 for the interim analysis - 0.045 for the final analysis 
Assumptions for calculating the required sample size:
 
 - At baseline, the standard deviation of NRS pain score is estimated at 2.0. - The expected mean difference in NRS (Capsaicin – Pregabalin) is 0. - The non-inferiority margin is set at +0.4 points on the NRS. - One-sided alpha risk: 4.5%. - Statistical power: 80%. 
Under these assumptions, 322 patients per arm are required (644 total). Considering a 20% rate of non-evaluable patients at 6 months, the total required sample size is 772 patients (386 per arm).

----------------------------------	---

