DESCRIPTION OF ANALYSIS SETS	
Description of planned statistical methods
 
A descriptive analysis of the study sample will be performed. Data will be presented as follows:
 
 • Qualitative variables: expressed as percentages. • Quantitative variables: expressed as mean and standard deviation, or median and range, depending on the distribution. 
Comparisons will be performed as follows:
 
 • Qualitative variables: using the Chi-square test or Fisher's exact test when appropriate. 
Quantitative variables: using Student's t-test or a non-parametric test (Wilcoxon test) depending on distribution and normality assumptions.
 
Definition of Analysis Populations
 
 • The ITT population includes all randomized patients in the CAPTRANE study. Patients are analyzed according to the treatment arm to which they were randomized, regardless of the treatment actually received. • Modified Intention-to-Treat Population (mITT) • The mITT population includes all randomized patients who received at least one administration of study treatment; i.e., excluding patients withdrawn prematurely or incorrectly included before receiving treatment. Patients are analyzed according to their allocated arm, regardless of treatment actually received. • Per-Protocol Population (PP) • The PP population includes all randomized patients who received the allocated treatment according to the protocol. Patients who received any treatment other than that assigned are excluded from the analysis. • If non-inferiority is demonstrated at the pre-specified 0.4 threshold (primary endpoint in the PP population), a Student's t-test will be used to compare the mean 24-hour maximum NRS pain scores at T2 (2 months after randomization) between the capsaicin and pregabalin arms, in the mITT population. • Mean 24-hour NRS scores at T6 will be compared between arms using a Student's t-test. • The percentage of patients with at least a "notable improvement" (PGIC score ≥ 5) will be compared between arms using a Chi-square test. • Reduction in painful area will be expressed as a percentage relative to baseline. • Differences in painful area between T2–T0 and T6–T2 will be compared using a Student's t-test. • All grade ≥ 2 adverse events will be described by category and by treatment arm. • The number of patients experiencing at least one grade ≥ 2 toxicity event will be compared using a Chi-square test. • The percentage of patients with $\geq 5\%$ weight gain will be compared between arms using a Chi-square test. • A subgroup analysis of NRS pain scores at T2 and T6 will be performed among patients with probable anxiety disorder and those with probable depressive disorder according to baseline HADS scores. • A multivariable linear regression model will be used to estimate the impact of pain duration before inclusion (expressed in months) on pain intensity at T2 and T6 (NRS), adjusted for:

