------------------------------	---

	
 - baseline NRS pain score, - treatment arm. 
Statistical stopping rules
 
An interim analysis will be conducted after inclusion of 150 patients per arm based on the primary endpoint (NRS at T6).
 
If a statistically significant difference in efficacy is observed at $\alpha = 0.005$, the study will be stopped for efficacy, regardless of which treatment demonstrates superiority.
 
Handling of missing, unused, or invalid data
 
Missing data for the numerical pain scale (NRS), painful area, and PGIC will not be imputed.
 
The proportion of missing data will be compared between arms using a Chi-square test.
 
Baseline characteristics of patients with missing data will also be compared.
 
Missing data for quality-of-life questionnaires (QLQ-C30, QLQ-BR23, EQ-5D) may be imputed according to EORTC manual recommendations.
 
Management of amendments to the analysis plan
 
Modifications to the statistical analysis plan may be proposed by the data monitoring committee (interim analysis, statistical tests, adverse event review, secondary objectives) if justified by emerging literature.
 
Protocol deviations will be identified and quantified.
 
Randomisation
 
Patients with a positive DN4 score will be randomized directly through the eCRF to be allocated to one of the following treatment arms:
 
 - Arm A (experimental): CAPSAICIN (patch), application of capsaicin patches to the painful area for 1 hour, with applications repeated every 3 months. - Arm B (standard): PREGABALIN (oral), oral pregabalin with progressive dose escalation. 
Validation of the randomization will automatically generate a confirmation email specifying the treatment arm allocated to the patient.
 
Randomization will be performed using balanced block allocation, stratified according to the following factors:
 
 - Study center - Pain intensity on the numerical rating scale (≥ 5) - Age (≥ 65 years) - HADS score (Incomplete, ≤ 18, > 18) - Pain duration (< 3 months or ≥ 3 months)
--	---

G) STUDY CALENDAR

DURATION OF INCLUSION PERIOD	36 months
TREATMENT DURATION	6 months
POST TREATMENT FOLLOW UP	6 months
STUDY COMPLETION DURATION (INCLUDING FU PERIOD)	42 months

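### The 6-month painful-area objective has no matching test: the later contrast named is T6–T2, which can hide or reverse a month-6 difference from baseline

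*Combined protocol and SAP*

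**What the plan says.** In section C, the table of secondary objectives and endpoints states the aim: "To compare the reduction of the painful area between the two arms after 2 and 6 months of treatment". The same row schedules the maps: "The painful area is measured using pain mapping at baseline (T0), and after 2 months (T2) and 6 months (T6) of treatment". Its evaluation-time column, however, gives only 2 months.

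Section F (planned statistical methods) has two consecutive lines on area. The first sets the scale: "Reduction in painful area will be expressed as a percentage relative to baseline". The second names the test: "Differences in painful area between T2–T0 and T6–T2 will be compared using a Student's t-test". That sentence does not itself say that the comparison is between arms; I read it so because the objective does. No line names a test of T6 against T0 for area.

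On missing maps, section F says: "Missing data for the numerical pain scale (NRS), painful area, and PGIC will not be imputed".

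**The concern.** The 2-month half of the objective has a matching test, T2–T0. The 6-month half does not. T6–T2 is the further change after month 2. It starts from a value measured after randomisation, which treatment may already have altered, and it answers whether the area kept shrinking or grew back. That is a reasonable thing to describe, but it is not the reduction achieved by month 6.

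The plan treats pain intensity differently: T6 scores are compared between arms directly. Of these two outcomes, only area takes month 2 as the starting point for its later comparison.

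At stake is what the trial reports about painful area at 6 months. If the plan is followed literally, the later test could show no difference where one exists, or point to the arm whose area is larger at month 6.

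**Working it through.** **1. The plan's own figures.** The documents give no figure for painful area: no expected reduction, no standard deviation, no power. The one design figure that can be reproduced is the sample size for pain intensity. Its inputs, all from section F, are an SD of 2.0, no true difference between arms, a margin of 0.4 points, 80% power and a one-sided alpha of 4.5%. Then n per arm = 2 × 2.0² × (1.695 + 0.842)² / 0.4² = 50 × 6.436 = 321.8, rounded up to 322, as stated. This figure has no bearing on the area endpoint.

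**2. Objective and test side by side.**

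| Question in section C | Contrast that answers it | Contrast named in section F |
|---|---|---|
| Reduction after 2 months | T2–T0 | T2–T0 |
| Reduction after 6 months | T6–T0 | T6–T2 |

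**3. How the contrasts relate.** For each patient, T6–T0 = (T2–T0) + (T6–T2), so T6–T2 = (T6–T0) − (T2–T0). This holds in area units, and also in percentages as long as both changes are taken relative to the baseline area. The same relation holds for between-arm differences in means. Writing D for arm 1 minus arm 2 (negative favours arm 1), D(T6–T2) = D(T6–T0) − D(T2–T0).

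Suppose arm 1 is ahead at month 2, so D(T2–T0) is negative. Then:
- if arm 1 has the same lead at month 6, D(T6–T2) is 0 and the lead is hidden;
- if arm 1 has a smaller lead at month 6, D(T6–T2) is positive and favours arm 2;
- if the arms are equal at month 6, D(T6–T2) favours arm 2 although there is no difference.

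**4. Illustration.** The mean areas below are assumed, as a percentage of baseline; none comes from the documents. Arm 1 goes 100→50→50. Arm 2 goes 100→80→X, with X varied to show the range.

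| X | D(T2–T0) | D(T6–T2), as planned | D(T6–T0) |
|---|---|---|---|
| 50 | −50 − (−20) = −30 | 0 − (−30) = +30 | −50 − (−50) = 0 |
| 60 | −30 | 0 − (−20) = +20 | −50 − (−40) = −10 |
| 70 | −30 | 0 − (−10) = +10 | −50 − (−30) = −20 |
| 80 | −30 | 0 − 0 = 0 | −50 − (−20) = −30 |

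At X = 60 and X = 70 the planned contrast favours arm 2, although arm 1 has the smaller area at month 6. At X = 80 it shows nothing, although the arms differ by 30 points. At X = 50 it shows a 30-point difference where month 6 has none.

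**5. Missing maps.** With no imputation, T6–T2 needs both a T2 and a T6 map. A patient with T0 and T6 maps but no T2 map is lost to T6–T2, yet could contribute to T6–T0.

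**The case against.** The best defence is that the plan already covers month 6 against baseline. Reduction is to be expressed relative to baseline, maps are taken at T6, and section F has a general rule that quantitative variables are compared by Student's t-test or Wilcoxon. On that reading T6–T2 is an extra interval comparison. This does not hold up. The percentage line sets a scale and names no test, and the line specific to this endpoint then names its two contrasts, of which T6–T0 is not one. A statistician following the text would run T6–T2.

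A second argument is that T2–T0 credits early shrinkage and that the two intervals sum to T6–T0. The first part is right, and it confines the problem to the 6-month question. The second holds for estimates in patients with all three maps, but two separate t-tests are not a test of the sum.

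It is also fair to say that T6–T2 has a use as a description of maintenance, and that a t-test on change from baseline is valid in a randomised comparison. Both points stand.

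**Conclusion.** The mismatch is plain in the text and rests on no assumption: the objective asks for the reduction at 2 and 6 months, and the later test named measures something else. Its numerical size cannot be given, because the trajectories above are assumed. They show what the contrast can do, not what it will do here.

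Three stronger conclusions are tempting and are not supported:

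- *The arm that responds early will look worse.* This happens on T6–T2 only if the other arm shrinks more after month 2. If both are stable after T2, the early advantage is hidden rather than reversed.
- *The capsaicin arm is the one disadvantaged, as a single application set against gradual pregabalin titration.* Section E (therapeutic schema) schedules applications every 90 days, so a second one can fall at about month 3, between T2 and T6. Whether one application suffices is itself an outcome to be estimated in that arm. The documents give no onset data for area, so the direction is unknown.
- *A t-test is unsuitable because areas are skewed.* The documents say nothing about the distribution, and the general rule in section F allows a Wilcoxon test.

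The consequence is limited to one secondary endpoint. The primary non-inferiority comparison and the sample size are unaffected.

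**What to change.** In section F, replace T6–T2 with T6–T0 as the 6-month comparison, and state that both T2–T0 and T6–T0 are compared between arms as percentage change from baseline. Keep T6–T2, if wanted, as a descriptive summary of maintenance with no test. In section C, change the evaluation time for this endpoint from 2 months to 2 and 6 months.

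Adjusting for baseline area by ANCOVA is an optional gain in precision and is not needed to correct the error.

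The cost is a few words: maps at T0, T2 and T6 are already planned, so no visit or measurement is added. The change should be made before the area data are analysed, because choosing T6–T0 afterwards would be post hoc.

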Systemic analgesics may be poorly tolerated due to side effects that can compound those of cancer treatments. For example, breast cancer patients receiving hormone therapy may experience menopausal-like symptoms including weight gain. Tricyclic antidepressants and pregabalin can also cause weight gain. According to the 2007 French Health Authority report, weight gain affects 3.5% of patients receiving pregabalin at 600 mg/day (15). Adverse effects from hormone therapy and neuropathic pain management may therefore add up and should be considered when developing the therapeutic strategy.

According to good practice recommendations from the French Society for the Study and Treatment of Pain, the choice of treatment depends on clinical context, comorbidities, safety profile, and cost (lower for tricyclic antidepressants) (16).

Topical Treatments

Systemic treatments may be combined with topical therapies such as lidocaine or capsaicin patches.

5% Lidocaine Plasters (VERSATIS®)

Lidocaine 5% plasters (VERSATIS®) received a European marketing authorization in 2007 for the treatment of post-herpetic neuralgia in patients with mechanical allodynia. The topical formulation is useful when systemic treatments are contraindicated. Tolerance is excellent, with minimal adverse effects compared to systemic treatments (17).

8% Capsaicin Patches (QUTENZA®)

Capsaicin 8% patches (QUTENZA®), marketed in France since 2011, are an innovative treatment for localized postsurgical neuropathic pain. Capsaicin is an agonist of the transient receptor potential vanilloid 1 (TRPV1) channel. It is indicated for the treatment of peripheral neuropathic pain in adults, alone or in combination with

other analgesics (1). The patch is applied to the most painful intact skin areas for 60–90 minutes, up to four patches simultaneously. Applications may be repeated every 90 days if needed. Application must be performed by a physician or healthcare professional in a hospital setting. Its major advantage lies in its low rate of adverse effects (10%), mostly mild erythema, burning sensations, or pruritus at the application site (1). Furthermore, the effect is long-lasting. Recent studies have demonstrated the superiority of capsaicin over pregabalin in treating allodynia in peripheral neuropathic pain (18).

Chronic Neuropathic Pain After Breast Surgery for Breast Cancer

Chronic Postsurgical Neuropathic Pain: A Frequent Symptom

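### The weight objective concerns change at 6 months, but the only weight-specific analysis is a chi-square test on gains of 5% or more, which answers it only in part

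*Combined protocol and SAP*

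**What the plan says.** Section C, under Secondary Objectives and Endpoints, sets this objective: "To compare weight change between the two arms after 6 months of treatment". The paired endpoint is "Weight is collected at T0, T2, and T6", with an evaluation time of 6 months. Neither entry names a threshold or a summary measure.

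Section F, in the row on analysis sets and planned methods, contains one line about weight: the percentage of patients with a gain of at least 5% is the outcome, and this "weight gain will be compared between arms using a Chi-square test". The line gives no visit, analysis set, reason for the 5% cut, effect estimate or confidence interval.

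The same row opens with a general rule: "Quantitative variables: using Student's t-test or a non-parametric test (Wilcoxon test) depending on distribution and normality assumptions". It does not mention weight.

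The background (section B, Systemic Treatments) notes that pregabalin and tricyclics can add to weight gain from hormone therapy. It gives the only weight figure in the documents: "weight gain affects 3.5% of patients receiving pregabalin at 600 mg/day". How gain was defined there is not stated. No power or sample size is claimed for weight.

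**The concern.** The objective asks how weight changed and how the arms differ. The named analysis reduces a continuous measurement to yes or no at one cut. A patient who loses 4%, one who is stable and one who gains 4% are all counted alike. The result is a p-value for two proportions. It does not say how many kilograms separate the arms or how precisely that is known.

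This matters because the background raises weight gain as something to weigh when choosing therapy. The primary test is for non-inferiority, and its planning assumption is "The expected mean difference in NRS (Capsaicin – Pregabalin) is 0". If pain outcomes turn out similar, differences in tolerability will carry more of the comparison. A cut-off can also cost power when the drug moves the whole distribution, particularly if few patients cross the cut.

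**Working it through.** **The plan's own sample size.** It concerns pain, not weight, but it fixes the number of patients. Inputs from section F: "the standard deviation of NRS pain score is estimated at 2.0", expected difference 0, margin 0.4, one-sided alpha 4.5%, power 80%.

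n per arm = 2 × [2.0 × (z(0.955) + z(0.80)) / 0.4]² = 321.8, so 322. This reproduces the plan's figure.

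**Patients available at T6.** 772 are randomised, "allocated into two balanced groups", with 20% non-evaluable at 6 months: 772 × 0.8 / 2 = 308.8, about 309 per arm.

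**Assumptions for weight (none are in the documents).** Percent change from T0 is normal; the reference arm has mean 0; the SD is 3%, 4%, 5% or 6%; the test is two-sided at 5%.

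**Scenario A: every patient in one arm shifts by the same amount.** The shift d is set so that the mean comparison has 80% power:

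d = SD × √(2/309) × (1.960 + 0.842)

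The proportions at or above 5% follow as p0 = 1 − Φ(5/SD) and p1 = 1 − Φ((5 − d)/SD). Chi-square power is Φ[(p1 − p0 − 1.960 × se0) / se1], where se0 uses the pooled proportion and se1 the separate ones.

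Worked for SD 4%: d = 4 × 0.08045 × 2.802 = 0.90; p0 = 10.6%, p1 = 15.3%; se0 = 0.0270, se1 = 0.0269; power = Φ[(0.0471 − 0.0529) / 0.0269] = Φ(−0.21) = 42%.

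| SD | Shift d | p0 | p1 | Mean comparison | Chi-square | n per arm for 80% by chi-square |
|---|---|---|---|---|---|---|
| 3% | 0.68 | 4.8% | 7.5% | 80% | 29% | 1241 (4.0 × 309) |
| 4% | 0.90 | 10.6% | 15.3% | 80% | 42% | 795 (2.6 × 309) |
| 5% | 1.13 | 15.9% | 21.9% | 80% | 49% | 654 (2.1 × 309) |
| 6% | 1.35 | 20.2% | 27.2% | 80% | 53% | 591 (1.9 × 309) |

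**Scenario B: only some patients gain.** A fraction q of the pregabalin arm gains an extra g, and the rest are unchanged. The mean difference is q × g, and the variance in that arm is SD² + q(1 − q)g².

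Worked for SD 3%, q = 10%, g = 7%:
- p0 = 4.8%; p1 = 0.9 × 4.8% + 0.1 × 74.8% = 11.8%; chi-square power 89%.
- Mean difference 0.7; averaged SD = √((9 + 13.41)/2) = 3.35; power = Φ[0.7 / (3.35 × 0.08045) − 1.960] = 74%.

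With SD 4% and the same q and g, the chi-square test has 57% and the mean comparison 53%. With SD 5.7%, q = 10% and g = 10%, the order turns: 46% for the chi-square test and 53% for the mean comparison.

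**Reading.** Which test is stronger depends on the shape of the effect and on the SD. The documents settle neither. The gap between objective and analysis does not depend on any of these numbers.

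**The case against.** The strongest reply has four parts.

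- **The objective names no summary measure.** A proportion gaining at least 5% is a between-arm comparison of change from T0, and it fits a directional safety question. The background's only figure is also a percentage of patients affected. This stands. A reader might infer that the planned test fails to answer the objective; the documents support only that it answers part of it.
- **Weight is quantitative, so the general t-test or Wilcoxon rule could cover it.** This stands to the extent that one cannot say the plan excludes a continuous comparison. It does not close the gap: section F goes on to assign tests endpoint by endpoint, and the line for weight is the chi-square test. At best two analyses of one objective are possible, and the plan does not say which applies.
- **The power loss is assumed.** This stands. A reader might infer that the trial is likely to miss a real weight difference. The documents give no weight SD or expected difference, and scenario B shows that the chi-square test can be the better one.
- **Weight is one of many secondary objectives, with no claimed power.** This stands. A reader might also take weight gain to be the background's main argument against pregabalin. It appears there as one example of additive effects, and for tricyclics too. The endpoint for the safety objective is grade 2 or higher adverse events.

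**Conclusion.** The point holds as a partial mismatch between objective and analysis. The objective is weight change after 6 months. The only weight-specific analysis counts gains of at least 5%, at no stated visit, and yields neither a mean difference nor a confidence interval.

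The effect on power is illustrative only. It falls from 80% to about 29% to 53% if the whole distribution shifts, with 309 per arm, SD 3% to 6% and reference mean 0. The loss shrinks or reverses if a minority accounts for the gain. The case for change therefore rests on answering the stated objective and reporting precision, not on a claim that the chi-square test is the weaker one. The primary conclusion is unaffected.

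**What to change.** Add to the planned analyses in section F: weight at T6 is analysed with a linear model on treatment arm and T0 weight, reporting the adjusted mean difference between arms and its 95% CI. Keep the comparison of the percentage with at least 5% gain, state that it refers to change from T0 to T6, and label it a supportive safety summary. Reporting both covers a general shift as well as gain confined to a few patients.

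This is a free improvement: it takes a line or two of text, uses weights already collected, removes no planned analysis and leaves the sample size unchanged. It should be written in before between-arm weight data are seen.
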